4.1.2 Acute Treatment (Randomization) Phase

If the subject meets all eligibility criteria, they will be randomized at the Baseline Visit via the IWRS. The subjects will be provided with an eDiary. Study personnel will educate the subject on the proper use of the eDiary, accurate reporting, and placebo response prior to the subject leaving the office.

After randomization via the IWRS, the subject will be dispensed a single dose of the double-blind study medication to take home for up to 45 days. This study medication is to be taken when an TMD-associated pain in the jaw and/or temple area on either side which reaches pain intensity of # 6 on the NRS (0-10) in the eDiary. The subject will be instructed to take their study medication, as an outpatient, when (if) they have an TMD-associated pain in the jaw and/or temple area on either side which reaches pain intensity of # 6 on the NRS (0-10) after they answer eDiary questions about their current pain and symptoms. The subject will complete an eDiary for 24 hours after taking study medication to record efficacy and other quality of life measures.

Subjects in this study may be randomized only once. Under no circumstances may a subject be re-randomized.

4.1.2.1 eDiary Data Collection

Subjects will record efficacy and other quality of life measures in their eDiary. This includes the following: onset time of TMD-associated pain, intensity of the TMD-associated pain prior to and at time of taking study medication. The subjects should not dose with study medication until the TMD-associated pain in the jaw and/or temple area on either side which reaches pain intensity of # 6 on the NRS (0-10). TMD-associated pain severity will be recorded using a NRS (0-10) at the onset of the pain and after dosing at time points of 15, 30, 45, 60, and 90 minutes and 2, 4, 8, and 24 hours. Subjects will record the date and time study therapy was taken in their eDiary according to the eDiary vendor's specifications. **CC1**

After dosing with study medication, all other medication to relieve TMD-associated symptoms is prohibited during the 2 hours post dose. At the end of 2 hours after dosing with study medication (and after the 2-hour assessments have been completed on the eDiary) subjects will be permitted to use the following rescue medication: acetaminophen (up to 1000 mg/day); or aspirin, ibuprofen, naproxen (or any other type of non-steroidal anti-

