6.4.2 Rescue Medication

The subject’s use of rescue medication is recorded by the subject in a paper diary.

CCI

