A by-subject listing is prepared that indicates the study drug exposure and accountability status for the treated analysis set; this listing includes study drug start date/time and study day, drug accountability kit dispensed date, kit returned date, kit ID, and IP used status (IP taken, IP not taken). A patient identifier listing is prepared if subjects had unknown exposure data, unknown accountability data, or for whom the exposure and accountability data did not match.

6.2.6.3 *Concomitant and Rescue Medications*

Concomitant non-study medications are tabulated by therapeutic class and preferred name for the treated analysis set. The definition of concomitant medication in Section 6.2.6.3 of the Core SAP, as applicable to single-dose studies, applies. For clarity, concomitant medications include

both medications recorded on the Concomitant Medications CRF that meet the definition of “concomitant” (see Section 6.2.6.3 of the Core SAP) and all rescue medications (defined below). Sites are instructed to exclude medications reported on the Rescue Medication CRF from the Concomitant Medications CRF.

Medications are displayed in descending order of overall frequency within therapeutic class and preferred name. Refer to the Sections 6.2.6.3 of the Core SAP for non-study medication counting rules in frequency tables.

Rescue medications include any non-study medication recorded on the Rescue Medication CRF with complete medication dates, and either (1) medication date/time is after the study drug start date/time if the medication time and study drug start time are both not missing, or (2) medication date is on or after study drug start date if the medication time or study drug start time is missing. Rescue medication dates are not imputed. Rescue medication times are not imputed, except as provided in Section 7.1.5 for time-to-event analyses. Rescue medications are separately tabulated and displayed in descending order of overall frequency within therapeutic class and preferred name for the treated analysis set. Any medication recorded on the Rescue Medication CRF that does not meet the above definition of a “rescue medication” will be treated as a current or concomitant medication, as appropriate, based on the imputed medication start date.

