6.3 Efficacy

Unless otherwise noted, all efficacy analyses are conducted using the treated analysis set as outlined below. Efficacy tabulations present results by as-randomized treatment group only (excluding overall), unless specified otherwise. All key efficacy data are included in listings by subject, treatment group, and time point (as applicable).

Summary statistics (n, mean, median, SD, minimum, maximum) are reported for continuous variables at each time point, along with change from baseline, as applicable.

6.3.1 **Rescue Medication**

Rescue medications are defined in Section 6.2.6.3. For efficacy evaluations (except for the analysis set forth in Section 6.3.3.6), a rescue medication is considered used as of a given time point if the date/time of first rescue medication use is on or prior to the date/time of that efficacy evaluation or, if the eDiary assessment is missing at that time point, if the date/time of first rescue medication use is :S the upper limit of the window for that assessment as specified in Table 5. For instance, a subject is treated as having used rescue medication as of 2 hours post-dose if the date/time of first rescue medication use is prior or equal to the date/time of the 2-hour assessment, even if the date/time of first rescue medication is more than 2 hours post-dose, or, if the eDiary assessment at 2 hours is missing, if the date/time of first rescue medication use is :S 135 minutes. If the time of first rescue medication is missing, the rescue medication is considered used as of a given time point if the date of rescue medication is on or prior to the date of that efficacy evaluation.

For efficacy evaluations (except for the analysis set forth in Section 6.3.3.6), the first rescue medication date/time is defined as the earliest rescue medication date/time, where missing time is considered to be earlier than non-missing time on the same date.

For clarity, assessments after rescue medication administration are not set to missing for purposes of calculating summary statistics, even when the assessments are set to missing for model evaluation.

6.3.2 **Primary Efficacy Endpoint**

6.3.2.1 **Primary Analysis**

TMD pain is assessed using an NRS score ranging in integers from 0 to 10, with 0 being “no pain” and 10 being “worst imaginable pain.” Each subject indicates pain using the eDiary at each of the following nominal timepoints: 0 (baseline), 15, 30, 45, 60, 90 and 120 minutes post-dose.

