The pain intensity difference at each post-baseline timepoint (PID_i) is calculated by finding the difference between the NRS score at each timepoint (PI_i) from the baseline NRS score (PI_0).

$$PID_i = PI_i - PI_0$$

The SPID-2 will be calculated by multiplying the PID score at each post-dose timepoint by the duration (in hours) since the preceding timepoint, then summing the values over the 2 hours.

$$SPID - 2 = \sum_{i=1}^6 (T_i - T_{(i-1)}) * PID_i$$

Where $T_0 = 0$, T_i = the nominal time as described in Table 3, $T_{(i-1)}$ = the preceding nominal time, PID_i = PID score at time T_i

Table 3: NRS Collection Nominal Timepoints

NRS collection timepoint	i	T_i (hours)
15 minutes	1	0.25
30 minutes	2	0.50
45 minutes	3	0.75
60 minutes	4	1.00
90 minutes	5	1.50
2 hours	6	2.00
4 hours	7	4.00
8 hours	8	8.00
24 hours	9	24.00

The SPID-2 will be analyzed on the treated population using an analysis of covariance (ANCOVA) model, estimated by Restricted Maximum Likelihood (REML) that includes baseline NRS value as a covariate and treatment group and stratification factor (use of daily medications / oral devices to reduce the intensity of TMD symptoms) as the main effects. The least squares mean (LS mean), standard error (SE), and 95% confidence intervals (CI) for each treatment group will be estimated and reported, as well as the LS mean, SE, and 95% CI for the difference between treatment groups (rimegepant – placebo). Descriptive summaries of PID value at each measured timepoint will be presented by treatment group to include mean, SD, median, minimum, and maximum.

The intercurrent events of non-study rescue medication and failure to log NRS pain score are treated with a composite strategy. All assessments after rescue medication administration are set to the last observation prior to the time of rescue medication use. Any missing NRS assessment(s) will be imputed to the last non-missing observation prior to the missing assessment. For clarity, in the case of intermittent missing values, missing values will be imputed based on the last non-missing observation prior to the missing value or consecutive series of missing values; any subsequent non-missing values will not be imputed unless rescue medication was administered prior to that assessment. Subjects who mistakenly dose and thus have a missing baseline NRS assessment will have the missing baseline assessment imputed as the mean of the non-missing baseline assessments across subjects.

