6.3.3.3 Pain Freedom at 2 Hours

The number and percentage of subjects in the treated population that experience pain freedom at 2 hours post-dose are analyzed after first imputing missing data at 2 hours to be failure (NC [Non-completer] = F [Failure]). Additionally, subjects who use rescue medication on or before assessment of pain at 2 hours are also assigned as failures (RM [Rescue medication use] = F). If the time of first rescue medication is missing, subjects are considered as failures if the date of rescue medication is the same as the date of dosing.

The analysis is done using Mantel-Haenszel risk estimation after imputation is done, with the stratification factor as yes/no for use of daily medications / oral devices to reduce the intensity of TMD symptoms. If one category of stratification factor has sparse data (less than 5 subjects), then the stratification factor is removed. Pain freedom is defined as an NRS score of zero at 2 hours post-dose (yes or no).

Results presented from the analysis includes the following:

- Response rate (i.e., “n/N” and percentage), asymptotic standard error (ASE), and 95% CI by randomization stratum for each treatment group
- Response rate (i.e., “n/N” and percentage), ASE, and 95% CI for each treatment group
- Percentage difference between treatment groups (rimegepant – placebo), ASE and 95% CI by randomization stratum
- Stratified percentage difference between treatment groups (rimegepant – placebo), ASE and 95% CI

A forest plot is produced depicting the risk difference for pain freedom at 2 hours post dose. The risk difference for each stratum will be presented, as well as the overall common risk difference.

6.3.3.4 *Time to Onset of Meaningful Pain Relief*

Time to onset of meaningful pain relief post-dose is analyzed descriptively for the treated population using Kaplan-Meier methods. Meaningful pain relief is considered the event in these analyses and is defined as the first nominal timepoint at which a 30% reduction of pain from baseline on the NRS is achieved. For clarity, meaningful pain relief is a 2-point reduction in NRS (0-10) score for subjects with a baseline pain score of 6, 7, or 8, and a 3-point reduction in NRS (0-10) score for subjects with a baseline pain score of 9 or 10.

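### A rescue entry with no clock time, dated on the dosing day, makes the SAP replace a compliant subject's observed 0–2 hour scores with baseline, so that SPID-2 becomes 0

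*SAP*

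**What the plan says.** - **Missing-time rule (SAP 6.3.1).** "If the time of first rescue medication is missing, the rescue medication is considered used as of a given time point", subject to the condition "if the date of rescue medication is on or prior to the date of that efficacy evaluation". The comparison is by calendar date only.
- **Ordering (SAP 6.3.1).** The first rescue is the earliest one, "where missing time is considered to be earlier than non-missing time on the same date".
- **What counts as rescue (SAP 6.2.6.3).** A complete date is required. An untimed entry qualifies if the "medication date is on or after study drug start date if the medication time or study drug start time is missing". Rescue dates are not imputed, and rescue times are imputed only for time-to-event analyses.
- **Consequence for SPID-2 (SAP 6.3.2.1).** "All assessments after rescue medication administration are set to the last observation prior to the time of rescue medication use". SPID-24 (6.3.3.1) and the 2-hour change (6.3.3.2) inherit this.
- **Pain freedom (SAP 6.3.3.3).** With a missing time, "subjects are considered as failures if the date of rescue medication is the same as the date of dosing".
- **Conduct (Protocol 4.1.2.1).** After dosing, "all other medication to relieve TMD-associated symptoms is prohibited during the 2 hours post dose". Rescue is permitted only once the 2-hour eDiary assessments are complete.
- **Data source (Protocol 6.4.2).** The subject's "use of rescue medication is recorded by the subject in a paper diary", whereas eDiary scores carry the date and time at which they were saved (SAP 7.1.5).

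**The concern.** In SAP Table 1 the intercurrent event for the primary endpoint is rescue up to two hours after dosing. Protocol 9.4.2 and 9.4.6 replace only scores that follow the rescue. A subject who obeys the protocol takes rescue after the 2-hour diary. If that subject leaves the clock time blank on paper, SAP 6.3.1 moves the use ahead of the 15-minute diary and overwrites six time-stamped scores that came before it. A gap in a record made after the endpoint window thus removes valid data from inside it.

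Two further faults follow from the same text. An untimed entry outranks a timed one on the same date, so a subject with a timed first rescue at 6 hours and a second, untimed dose that evening also gets SPID-2 = 0. Around midnight, 6.3.1 (evaluation date) and 6.3.3.3 (dosing date) can classify the same subject differently. SAP version 2.0 dropped all sensitivity analyses, so no planned output would show the effect.

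**Working it through.** **Inputs.** The plan gives no figure for this rule. SAP section 5 gives 80 per arm, SD 3.0, a 2-point reduction on rimegepant and a 1.5-point advantage over placebo, which implies means of about −2.0 and −0.5. These inputs reproduce the stated power of roughly 88%: 1.5 / (3.0 × √(2/80)) = 3.16, and Φ(3.16 − 1.96) = 88.5% (88.2% with the t distribution). Reading these means as SPID-2 values is an assumption, as are all rescue and missing-time rates below.

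**One subject.** Assume a baseline of 8, then 7, 6, 5, 4, 3, 2 at 15, 30, 45, 60, 90 and 120 minutes. The observed SPID-2 is 0.25 × (−1 −2 −3 −4) + 0.5 × (−5 −6) = −8.0. Applying 6.3.1 and 6.3.2.1 to an untimed rescue entry:

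| Dosing time | Rescue dated | Scores used | SPID-2 |
|---|---|---|---|
| 10:00 | same day | 8, 8, 8, 8, 8, 8 | 0.0 |
| 20:00 | next day | 7, 6, 5, 4, 3, 2 | −8.0 |
| 22:30 | next day | 7, 6, 5, 4, 4, 4 | −6.5 |
| 23:10 | next day | 7, 6, 5, 5, 5, 5 | −5.25 |

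In the last two rows 6.3.1 flags the 2-hour evaluation, because it falls on the rescue date. The missing-time sentence of 6.3.3.3 does not, because the rescue date is not the dosing date.

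**One untimed same-day entry across the SAP.**

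| Section | Handling |
|---|---|
| 6.3.1 with 6.3.2.1, 6.3.3.1, 6.3.3.2 | used from 15 minutes; scores become baseline |
| 6.3.3.3 | not pain free, even with a recorded 0 at 2 hours |
| 7.1.5 (time to onset) | rescue placed at the dosing time |
| 6.3.3.6 | excluded, unless a timed use falls within 24 hours |

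**How often untimed rescue falls on the dosing date.** Assume dosing uniform over 0–24 h or 7–22 h on the clock. The same-date share is about 34–46% if rescue is spread evenly over 2–24 hours after dosing, and 83–87% if over 2–6 hours.

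**Effect on the treatment difference.** Let m be the arm mean, r the proportion with same-day later rescue, and q the share of those with an untimed entry. If rescuers have their arm's average SPID-2:

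reported difference = m_R(1 − r_R·q) − m_P(1 − r_P·q)

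With m_R = −2.0 and m_P = −0.5:

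| r_P, r_R | q = 0.10 | q = 0.25 | q = 0.50 |
|---|---|---|---|
| 30%, 30% | −1.455 | −1.388 | −1.275 |
| 50%, 30% | −1.465 | −1.413 | −1.325 |
| 50%, 20% | −1.485 | −1.463 | −1.425 |

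Every cell is attenuated, by 1% to 15%.

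**When it would inflate.** The formula equals −1.5 + q(|m_R|·r_R − |m_P|·r_P), so inflation needs r_P / r_R > |m_R| / |m_P|. With the planning means that ratio is 4. With assumed means of −3.5 and −2.0 it is 1.75; rescue of 50% against 20% and q = 0.5 then gives −3.5 × 0.90 + 2.0 × 0.75 = −1.65.

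**Weight of one subject.** Setting an assumed SPID-2 of −4 to 0 moves an arm mean by 4/80 = 0.05. The trial stopped early for low enrolment; at an assumed 20 per arm the shift is 4/20 = 0.20.

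**The case against.** - **Scope.** A reader might infer that any rescue entry without a time sets SPID-2 to 0. The date condition in 6.3.1 rules that out. Next-date entries change nothing unless the 0–2 hour window crosses midnight, and entries without a complete date are not rescue at all under 6.2.6.3. This limit stands.
- **Baseline is inferred.** SAP 6.3.2.1 refers to the time of rescue use, which is missing here. The imputation in 7.1.5 is reserved for time-to-event analyses, and the Core SAP, which governs where this SAP is silent, is not available. That is fair, but once 15 minutes is flagged, baseline is the only value left to carry forward.
- **Prespecified and cautious.** Counting untimed same-day use as failure fits the general failure approach to rescue, and assuming compliance cannot be verified either. On the planning means the rule does attenuate. It is not cautious for every subject, though: one who worsened over 2 hours is moved up to 0. Nor does caution justify overwriting scores that very likely preceded the rescue.
- **Size.** Rescue is meant for subjects without relief at 2 hours or whose pain returns. Those without relief would have SPID-2 nearer 0, so zeroing them changes less than the table shows. Protocol Table 1 has paper diaries reviewed with subjects at visits, which should keep missing times down. Both points stand.
- **Stakes.** SAP version 2.0 evaluates no significance, and observed scores stay in the summary statistics. That lowers the stakes, but the LS means and confidence intervals still rest on the overwritten scores.

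**Conclusion.** The concern holds for untimed rescue entries dated on the dosing day. For a compliant subject they turn permitted later rescue into the 0–2 hour event of Table 1, contrary to Protocol 9.4.2 and 9.4.6. They also set SPID-2 and the 2-hour change to 0 and make the subject a pain-freedom failure. The ranking of untimed over timed entries and the midnight mismatch are real as well, though the mismatch should be rare.

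The size is modest and uncertain. Under the stated assumptions the difference moves from −1.5 to between about −1.49 and −1.28, and probably less if rescuers had little relief by 2 hours. A reader might infer that the rule biases the result in either direction, or always hits the arm with more rescue harder. The planning figures do not support that: inflation needs a large placebo response together with a large imbalance in rescue, neither of which the documents suggest.

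**What to change.** 1. In SAP 6.3.1, where the 2-hour diary was saved and the only evidence of earlier rescue is an untimed entry on the dosing date, keep the observed 0–2 hour scores and treat the use as after the 2-hour assessment.
2. Use one date rule in 6.3.1 and 6.3.3.3, comparing with the date on which the 2-hour diary was saved. This is needed for late dosing: if that diary was saved after midnight, an entry dated on the dosing day really does precede it and should still count as earlier use.
3. Apply the rule to SPID-2, the 0–2 hour part of SPID-24, the 2-hour change and pain freedom. Align the imputed rescue time in 7.1.5, so that the same subject is not placed at dosing time for time to onset.
4. For 0–2 hours, do not let an untimed entry override a timed first use.
5. Query sites for missing rescue times before lock.
6. Report the current rule as a one-row sensitivity analysis of SPID-2.

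The cost is SAP wording, some site queries and one table row. The downside is that a true untimed breach before 2 hours would be kept as observed; the sensitivity row would show how much that matters.

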
6.3.3 Secondary Efficacy Endpoints

Secondary endpoints will be analyzed on the treated population.

6.3.3.1 Sum of Pain Intensity Difference at 24 Hours (SPID-24)

The analysis in Section 6.3.2.1 is repeated for the SPID-24 on the treated population, with SPID-24 being calculated by multiplying the PID score at each post-dose timepoint by the duration (in hours) since the preceding timepoint, then summing the values over a 24-hour period.

Each subject indicates pain using the eDiary at each of the following nominal timepoints: 0 (baseline), 15, 30, 45, 60, 90 and 120 minutes, and 4, 8, and 24 hours post-dose.

6.3.3.2 Change from Baseline of Pain on NRS at 2 Hours

Change from baseline pain on NRS score is analyzed on the treated population using a generalized linear mixed effect model that includes the baseline NRS (0-10) value as a covariate, and fixed effects for treatment group, stratification factor (use of daily medications / oral devices to reduce the intensity of TMD symptoms), scheduled time point, and time point by treatment group interaction. Time points included in the model are nominally at 15, 30, 45, 60, 90 and 120 minutes post-dose.

Repeated measures within subject are modeled using an unstructured covariance structure for within subject error. In the case the model fails to converge, a Huynh-Feldt error structure is utilized, followed by an AR(1) structure. Error degrees of freedom are calculated using the Kenward-Rogers approximation if an unstructured covariance structure fits appropriately; otherwise, a sandwich estimator is utilized to estimate the covariance structure, and the degrees of freedom are calculated using the between-within method.

Restricted maximum likelihood (REML) estimation is utilized; should the model fail to converge under REML, maximum likelihood estimation is utilized.

Least squares (LS) means, SE, and 95% CIs are reported for each treatment group at 2 hours post-dose, along with LS mean difference estimate (rimegepant - placebo) and associated SE and 95% CI.

Intercurrent events will be handled in the same way as in the primary analysis described in Section 6.3.2.1.

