9.4.3.2 Change from Baseline of Pain on NRS

The change from baseline of pain on NRS score at 2 hours post-dose will be analyzed with a generalized linear mixed effect model that includes subject as a random effect, the baseline NRS (0-10) value as a covariate, and fixed effects for treatment group, stratification factor (use of daily medications / oral devices to reduce the intensity of TMD symptoms), scheduled time point, and time point by treatment group interaction. Time points included in the model are nominally at 15, 30, 45, 60, 90 and 120 minutes post-dose. Repeated measurements within-subject will be modeled using an unstructured covariance structure for within-subject error. In the case that the model fails to converge, a Huynh-Feldt error structure will be attempted, followed by an AR(1) structure. Error degrees of freedom will be calculated using a Kenward-Roger approximation. The difference estimate (rimegepant - placebo), SE, 95% CI, and p-value will be reported for 2 hours post-dose.

Intercurrent events of use of a non-study rescue medication at or before 2 hours post-dose, or if a subject fails to log their pain score at any time after study drug is administered through 2 hours post-dose, will be handled in the same manner as they are for the primary endpoint.

9.4.3.3 *Pain Freedom at 2 Hours*

The number of subjects that are pain free at 2 hours post-dose will be analyzed after first imputing missing data at 2 hours to be failure (NC = F). Additionally, subjects who use rescue medication on or before assessment of pain at 2 hours will also be assigned as failures (RM = F). The analysis will be done using a stratified Cochran-Mantel-Haenszel (CMH) test after imputation is done, with the stratification factor as use of daily medications / oral devices to reduce the intensity of TMD symptoms.

9.4.3.4 *Time to Onset of Meaningful Pain Relief*

Time to onset of meaningful pain relief post-dose will be defined as the first nominal timepoint at which a 30% reduction of pain from baseline on NRS is achieved. This will be analyzed using Kaplan-Meier methods for a “time to event” analysis. Rimegepant will be compared to placebo using a log-rank test which will compare the survival distributions. Intercurrent events will be handled in the same manner as they are for the primary endpoint.

9.4.3.5 *Time to Onset of Initial Pain Relief*

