1 BACKGROUND AND RATIONALE

This document presents the statistical analysis plan (SAP) for Protocol BHV3000-317: A Phase 2/3, Double-Blind, Randomized, Placebo-Controlled, Safety and Efficacy Trial of BHV-3000 (rimegepant) Orally Disintegrating Tablet (ODT) for the Acute Treatment of Temporomandibular Disorders (TMD).

This SAP contains the analysis details and methodology to answer the study objectives, including planned tables, listings, and figures (TLFs), which provide the basis for the results section of the clinical study report (CSR).

The Rimegepant (BHV3000)/Zavegepant (BHV3500) Core Statistical Analysis Plan, v3.0 (the “Core SAP”) describes analysis details and methodologies common to the BHV3000 program and is incorporated by reference. The Core SAP assumes primacy for any matter where this SAP is silent (and the relevant content of the Core SAP could feasibly apply) or where the Core SAP is directly referenced as applicable. Otherwise, should any discrepancy exist between the Core SAP and this SAP, this SAP assumes primacy.

For purposes of applying the Core SAP, the following applies:

- BHV3000-317 is a single-dose study
- BHV3000-317 is not a study with a follow-up phase
- References in the Core SAP to “studies with a COVID-19 Visit Impact CRF” will not necessarily apply to BHV3000-317. COVID-19 impact will be addressed as specified in this SAP.

Note that the study was terminated prematurely in 1Q2023 due to low enrollment. As a result, the SAP is being amended from Version 1.0 to 2.0 to reduce the number of TLFs to focus only on the most important outputs.

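### If the unstructured model for 2-hour NRS change does not fit, the SAP's sandwich fallback names no small-sample correction, so its 95% interval could be too narrow with few treated subjects

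*SAP*

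**What the plan says.** SAP 6.3.3.2 fits a repeated-measures model to the change in NRS: "Time points included in the model are nominally at 15, 30, 45, 60, 90 and 120 minutes post-dose". The covariance is unstructured at first. "In the case the model fails to converge, a Huynh-Feldt error structure is utilized, followed by an AR(1) structure".

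The df rule has two branches. The first is "Error degrees of freedom are calculated using the Kenward-Rogers approximation if an unstructured covariance structure fits appropriately", and no criterion for an adequate fit is given. The second is "otherwise, a sandwich estimator is utilized to estimate the covariance structure, and the degrees of freedom are calculated using the between-within method". The section names no small-sample correction for the sandwich and does not say which df the 2-hour treatment contrast receives.

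The output is the LS mean, SE and CI per arm at 2 hours, "along with LS mean difference estimate (rimegepant - placebo) and associated SE and 95% CI". SAP section 5 says that the secondary endpoints will not be evaluated for significance.

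Protocol 9.4.3.2 lists the same three covariance structures and then says, without condition: "Error degrees of freedom will be calculated using a Kenward-Roger approximation". It has no sandwich step, so the SAP added the fallback.

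SAP section 1 says that "the study was terminated prematurely in 1Q2023 due to low enrollment". It also gives the Core SAP priority on matters where this SAP is silent. Neither document states how many subjects were treated.

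**The concern.** Kenward-Roger is the small-sample adjustment in this analysis, and the SAP gives it up when the preferred model does not fit. Two features of the replacement can shorten the interval when subjects are few.

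- The standard sandwich is built from residuals that are smaller than the true errors, because each subject pulls the fit towards itself. Its variance is therefore biased downward in small samples.
- Between-within splits the df into a between-subject and a much larger within-subject part. The 2-hour difference combines the treatment effect (between subjects) with the time-by-treatment interaction (within subjects). If it is given the within-subject df, the t multiplier is close to the normal value however few subjects there are.

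With no test planned, the interval is the only inferential statement for this endpoint. Overstated precision would pass to the reader unnoticed.

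**Working it through.** **1. The plan's own figure.** With 80 per arm, a difference of 1.5 and SD 3.0 (SAP section 5), SE = 3.0 × √(2/80) = 0.474. Then 1.5/0.474 − 1.96 = 1.20, which gives 88.5% power (88.2% with noncentral t on 158 df). The stated 88% for the primary endpoint is reproduced. Here it serves only to fix the planned size and the SD.

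**2. Parameters.** Six time points give 6 × 7/2 = 21 unstructured covariance parameters.

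**3. Degrees of freedom.** Let N be the total treated. Between-subject df are N − 4 (intercept, baseline, stratum, treatment). Within-subject df are 6N − N − 10 = 5N − 10 (five time and five interaction terms removed). At 5 per arm these are 6 and 40; at 10 per arm, 16 and 90.

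**4. Variance.** With A = Σ Xᵢ′WᵢXᵢ, where Wᵢ is the inverse working covariance and eᵢ the residuals of subject i, the standard sandwich is A⁻¹(Σ Xᵢ′Wᵢeᵢeᵢ′WᵢXᵢ)A⁻¹. With Hᵢ the leverage of subject i, the leverage-corrected form replaces eᵢ by (I − Hᵢ)^(−1/2)eᵢ. Mancl-DeRouen uses (I − Hᵢ)⁻¹eᵢ.

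**5. Simulation.** Complete data at six time points, baseline and stratum covariates, time and time-by-treatment, AR(1) working covariance. There were 3000 runs per size (1500 at 30 and 80 per arm); at 5 per arm 2795 were usable. Assumed, not from the documents: SD rising from 1.0 to 3.0 over 2 hours (only the 3.0 is in the SAP), lag-1 correlation 0.85, and 40% in the yes stratum.

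Coverage (%) of the nominal 95% interval for the 2-hour difference:

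| Per arm | Sandwich SE ÷ true SD | Standard, between df | Standard, within df | Leverage-corrected, between df | Mancl-DeRouen, between df |
|---|---|---|---|---|---|
| 5 | 0.74 | 89.8 | 83.5 | 94.2 | 97.0 |
| 8 | 0.84 | 91.4 | 88.6 | 93.9 | 96.3 |
| 10 | 0.88 | 92.6 | 90.5 | 94.2 | 95.7 |
| 15 | 0.92 | 93.3 | 92.4 | 94.7 | 96.0 |
| 20 | 0.95 | 93.6 | 93.0 | 94.5 | 95.3 |
| 30 | 0.94 | 93.3 | 92.9 | 93.7 | 94.7 |
| 80 | 0.97 | 94.5 | 94.4 | 94.5 | 94.6 |

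Monte Carlo error is about 0.4 points at nominal coverage (√(0.95 × 0.05/3000)) and 0.7 in the lowest cell (√(0.835 × 0.165/2795)).

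**6. Reading the table.** The shortfall from 95% is 5.2 to 11.5 points at 5 per arm, 2.4 to 4.5 at 10, 1.4 to 2.6 at 15 to 30, and 0.5 to 0.6 at 80. A per-time-point ANCOVA with t on N − 4 df, a stand-in for the unstructured model, covered 94.3-95.0% throughout. At 10 per arm its mean width was 5.97, against 5.18 (between df) and 4.85 (within df): 1 − 5.18/5.97 = 13% and 1 − 4.85/5.97 = 19% narrower.

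**7. Both parts of the remedy matter.** With within-subject df, the leverage-corrected sandwich still covered only 90.0% at 5 per arm and 92.9% at 10.

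**8. Other runs.** A separate simulation under two variance patterns gave about 83% (within df) and 89% (between df) at 5 per arm, 90-93% at 10 and 92-94% at 15 to 20. A bias-corrected sandwich with between-subject df gave 95-98%.

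**The case against.** **The SAP does not say the sandwich is uncorrected.** A reader might infer that it prescribes the plain version. It is only silent, and the Core SAP could name a correction. This stands: the coverage figures hold only if the standard form is used.

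**The fallback may rarely be used.** A reader might infer from the 21 parameters and the low enrolment that it is likely. The documents do not show that. Carrying the last value forward (SAP 6.3.2.1, applied here by 6.3.3.2) makes the six-point data complete, which helps convergence. In 300 simulated trials per size with complete integer NRS data (SD 1 to 3, lag-1 correlation 0.85, not fitted in SAS), the unstructured model fitted in 100% at 8, 10, 15 and 20 per arm, 99% at 6 and 64% at 5. With 10% of scores carried forward it fitted in 100% at 8 and 98% at 6; heavier carry-forward was not completed and could make adjacent time points nearly collinear at any N. What stands is that fallback appeared mainly at about 5 per arm. The coverages above are also not conditional on the unstructured fit having failed.

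**The sandwich improves on the protocol.** A reader might infer that leaving Kenward-Roger is the fault and that the protocol's rule should return. The numbers do not support that. Model-based AR(1) intervals (without Kenward-Roger) covered only 83-88% at every size when the true variance rose over time. Kenward-Roger does not repair a wrong covariance structure. Huynh-Feldt was not simulated. The sandwich guards against a wrong structure and is worth keeping.

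**Conclusion.** The point holds conditionally. If the unstructured covariance does not fit, the standard sandwich is used and few subjects were treated, the 95% CI for the 2-hour difference is too narrow under either reading of the df. Coverage is about 83% to 89-90% at 5 per arm, 90-93% at 10, about 92-94% at 15 to 30, and near nominal at 80.

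This rests on assumed covariances, an AR(1) working structure and an unstated achieved N. It does not show that the reported interval is wrong, and the primary SPID-2 ANCOVA is untouched. One secondary, untested endpoint is affected: a cheap improvement.

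**What to change.** In SAP 6.3.3.2, keep the sandwich in the Huynh-Feldt and AR(1) fallback. Specify a bias-corrected version (for example Mancl-DeRouen or Morel-Bokossa-Neerchal) and state that the 2-hour treatment contrast takes between-subject df. If the Core SAP already names a correction, a cross-reference plus the df statement is enough. Do not revert to model-based Kenward-Roger with Huynh-Feldt or AR(1).

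The cost is one sentence, and somewhat wider, possibly slightly conservative intervals if the fallback is used (Mancl-DeRouen covered 97.0% at 5 per arm). At the planned size the change makes almost no difference.
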